2.4.4.2 Analyses of secondary efficacy endpoints

For continuous secondary efficacy endpoints (see Section 2.1.3) with missing data at Baseline, missing data will be imputed using MI under the assumption of missing at random (MAR). Missing data at Baseline will be imputed using regression method that includes randomization stratum of HbA1c ($\leq 8.5\%$, $> 8.5\%$), randomization stratum of sex (male, female) and baseline value in the imputation model.

Each continuous secondary efficacy endpoint (Section 2.1.3) will be analyzed using a similar ANCOVA model including the measurements at Baseline and endpoint (observed or imputed). The missing data at endpoint will be imputed by the retrieved dropouts if there are at least 5 patients in each study treatment group who discontinued but have the endpoint. Otherwise, the washout imputation method will be used. After the imputation, each of the complete datasets will be analyzed by an ANCOVA model with treatment groups (sotagliflozin 400 mg, sotagliflozin 200 mg, placebo), randomization stratum of HbA1c ($\leq 8.5\%$, $> 8.5\%$), randomization stratum of sex (male, female), and country as fixed effects, and baseline secondary endpoint value as a covariate.

Results from each complete dataset will be combined using Rubin's rule to provide the adjusted mean change from Baseline to week 26 (or week 12 for SBP) for each treatment group, as well as the between treatment group difference (comparing each sotagliflozin group to placebo group) and the 95% CI for the between-group difference.

For all continuous secondary endpoints, summary statistics at scheduled visits will be provided for each treatment group. The summary will include the number of observations, mean, SD, SE,

minimum, median, and maximum. Graphical presentations will also be used to examine trends over time using mean (\pm SE) and mean change from Baseline (\pm SE) at each of the scheduled visits. In addition, SBP will be summarized descriptively at each visit for those with baseline SBP \geq 140 mmHg.

Categorical endpoint of HbA1c $<$ 7% at week 26 will be analyzed using a Cochran-Mantel-Haenszel (CMH) method stratified by randomization stratum of HbA1c (\leq 8.5%, $>$ 8.5%), and randomization stratum of sex (male, female). Proportion of HbA1c responders in each treatment group will be provided with the difference between each sotagliflozin group and placebo group and their associated 2-sided 95% CI. To determine whether a patient is HbA1c responder or not, all measurements at week 26 will be used regardless of discontinuation of IMP or initiation of rescue medication. Patients with no HbA1c measurement at week 26 will be treated as non-responders. Summary tables and graphs will be provided by treatment group at scheduled visit.

For between-group comparison for HbA1c $<$ 7% responder analysis, a sensitivity analysis will be performed by excluding patients with baseline HbA1c $<$ 7% using the same CMH test mentioned above. Similarly, by-visit summary based on above subset of patients may be provided.

2.4.4.3 Analyses of other efficacy endpoints

The analysis of other endpoints (see [Section 2.1.3](#)) will be descriptive with no formal testing. Summary statistics at scheduled visits based on observed value will be provided by each treatment group. Graphical presentations will also be used to illustrate trends over time.

The number (%) of patients who used rescue therapy will be summarized by treatment group during the 26-week core (see [Section 2.5.4](#)) and the 104-week entire double-blind treatment periods. A KM curve for the time to first rescue therapy will be presented during the 26-week core treatment period and 104-week entire double-blind treatment period (see [Section 2.5.4](#)). The list of patients who used rescue therapy will also be provided.

UACR will be log-transformed at patient level. Summary statistics of UACR in log scale will be calculated for each treatment group at each visit and back-transformed to provide the geometric mean and its associated percent change of UACR from Baseline.

Shift tables will be provided for UACR at Week 26 and Week 104 respectively using the pre-defined categories. That is, the number (%) of patients with progression from one category at Baseline to another category at Week 26 and Week 104 will be provided by treatment group. The pre-defined categories are, for UACR, $<$ 30 mg/g creatinine [Normal], \geq 30 to $<$ 300 mg/g creatinine [Microalbuminuria], and \geq 300 mg/g creatinine [Macroalbuminuria].

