## 11.4 STATISTICAL METHODS

Continuous data will be summarized by treatment group using the number of observations available (N), mean, SD, minimum, median, and maximum.

Categorical data will be summarized by treatment group using count and percentage.

In general, descriptive statistics of quantitative efficacy and safety parameters (result and change from Baseline) by scheduled visits will be provided on observed cases (OC), ie, inclusion of only patients having nonmissing assessments at a specific visit.

The Baseline value is defined generally as the last available value before the first dose of double-blind IMP or the last available value prior to randomization for patients who were randomized but never exposed to IMP.

For serum creatinine and eGFR, the Baseline value is defined as average of all values before the first dose of double-blind IMP for those randomized and exposed or before randomization for patients who were randomized but never exposed to IMP.

Analysis of demographics and Baseline characteristics and prior and concomitant medications will be provided in detail in the Statistical Analysis Plan (SAP).

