#### **11.4.2.3 Analysis of other efficacy endpoints**

The analysis of other efficacy endpoints will be descriptive with no formal testing. Summary statistics at scheduled visits using OC will be provided by each treatment group. Graphical presentations will also be used to illustrate trends over time

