1.2.3 Other objectives

Other objectives of this study are to compare the effects of sotagliflozin 200 mg and 400 mg versus placebo with respect to:

- Change from Baseline to Weeks 52 and 104 in HbA1c.
- Change from Baseline to Weeks 52 and 104 in FPG.
- Change from Baseline to Weeks 52 and 104 in BW.
- Proportion of patients with HbA1c <7.0% at Weeks 52 and 104.
- Proportion of patients starting rescue therapy for hyperglycemia during the 104 weeks of treatment.
- Change from Baseline to Weeks 26 and 104 in SBP for all patients.
- Change from Baseline to Weeks 12, 26, and 104 in SBP for the subsets of patients with Baseline SBP \geq 130 mmHg and <130 mmHg, respectively.

- Change from Baseline to Weeks 12, 26, and 104 in diastolic blood pressure (DBP) for all patients and the subsets of patients with Baseline DBP ≥ 80 mmHg and < 80 mmHg, respectively.
- Changes from Baseline to Weeks 26, 52, and 104 in total body fat mass and total lean mass measured by DXA.
- Changes from Baseline to Weeks 26, 52, and 104 in serum estradiol (only for women).
- Changes from Baseline to Weeks 26, 52, and 104 in urinary albumin to creatinine ratio (UACR).
- Changes from Baseline to Weeks 26, 52, and 104 on estimated glomerular filtration rate (eGFR).

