2.1.3 Efficacy endpoints

All efficacy measurements collected during the study will be considered for analyses, including those obtained after IMP discontinuation or introduction of rescue therapy (see [Section 2.5.4](#)).

HbA1c, FPG, UACR, eGFR and serum estradiol are measured/calculated in a central laboratory (see study flowchart in Appendix D). Body weight, SBP and DBP (see [Section 2.1.4.5](#)) are measured at on-site visits by the investigator. Patients requiring rescue are identified as those with the reason for treatment ticked “rescue therapy” in e-CRF “Medication” page.

Efficacy variables will be summarized in both standard international units and conventional units when applicable.

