2.4.4 Analyses of efficacy endpoints

Efficacy analyses will be performed on the ITT population using the efficacy assessments collected during the study, including those obtained after IMP discontinuation or introduction of rescue therapy (de facto estimand), unless otherwise specified.

Statistical testing will be performed for primary endpoint and secondary endpoints at Week 26 (or Week 12 for SBP). The superiority tests will be two-sided tests at nominal 5% significance level. All efficacy endpoints, other than primary and main secondary efficacy endpoints, will only be summarized by descriptive statistics without formal statistical testing.

Missing data for efficacy analyses is identified through steps described in [Section 2.5.4](#).

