2. In cases that a non-monotone missing data pattern occurs at the intermediate visits, these data points will be imputed using the Markov Chain Monte Carlo (MCMC) option in PROC MI to partially impute missing data at the intermediate visits in order to achieve a monotone missing pattern for all patients. The imputation model will include treatment, BMD measurements at Baseline, Week 26, Week 52, and Week 104.
3. Using the partially and monotone data sets from the MCMC of step 2, the rest of the missing data will be imputed using a sequential imputation approach. Given that the data sets have monotone missing data pattern, the approach will be to consider imputation on a visit (timepoint) by visit (timepoint) basis and conditioning on all visits (timepoints) data. The process will be to repeat, sequentially, in the order specified in the regression model, the imputation of missing values at each visit (timepoint). The imputation model will include treatment, measurements at Baseline, Week 26, Week 52, and Week 104 in the VAR statement.

A top line analysis to evaluate the efficacy will be conducted when all patients have either completed Week 26 or discontinued prior to Week 26.

The imputation model at Week 26 for the topline analysis will include treatment and measurement at Baseline, after missing baseline data imputation as described in step 1 above.

The imputation method will generate multiple complete data sets. The change from Baseline to Week 26, Week 52, and Week 104 will be derived from observed and imputed BMD values.

The derived change from Baseline to each timepoint in each of the complete datasets will be analyzed by the ANCOVA model with treatment groups (sotagliflozin 400 mg, sotagliflozin 200 mg, placebo), randomization stratum of HbA1c ($\leq 8.5\%$, $> 8.5\%$), randomization stratum of sex (male, female), country as fixed effects, and baseline BMD value as a covariate.

Results from each complete data set will be combined using Rubin's rule to provide the adjusted mean change in BMD from Baseline to each timepoint (Week 26, Week 52, and Week 104) for each treatment group, as well as the between-group difference (comparing sotagliflozin 400 mg or sotagliflozin 200mg vs placebo) and the 95% confidence interval (CI).

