For the safety analyses, the baseline for a given parameter is defined as the last available measurement (or the average of all measurements for creatinine and eGFR), including unscheduled assessments, assessed prior to the first administration of double-blind IMP. For the efficacy analyses, the baseline for a given parameter is defined as the last available measurement (or the average of all measurements for eGFR), including unscheduled assessments, assessed prior to the first administration of double-blind IMP or the last available value (or the average of all measurements for eGFR) before randomization if not treated with double-blind IMP.

Summary statistics by visit for continuous efficacy endpoints

Summary statistics (number, mean, SD, SE, minimum, median, maximum) of continuous efficacy endpoints (observed data and change from Baseline) will be provided at scheduled visits as per protocol. Summaries showing data by visit will be presented according to the visit number (or re-allocated visit number, see [Section 2.5.4](#)) and labeled with the targeted approximate day/week.

Last on-treatment value for laboratory variables and vital signs

The last on-treatment value is the final measurement assessed during the treatment epoch, regardless of the introduction of rescue therapy, including measurements at unscheduled visits. See [Section 2.1.4](#) and [Section 2.5.4](#) for details.

Display of safety data by visit (laboratory variables and vital signs)

Descriptive statistics (number, mean, SD, minimum, median, maximum) of quantitative laboratory variables and vital signs (observed data and change from Baseline) during the TEAE period will be provided at scheduled visits. In addition, these summaries will also include a row for the 'last value on-treatment' to describe the last available on-treatment value (see above). Summaries showing data by visit will be presented according to the visit number (or re-allocated visit number, see [Section 2.5.4](#)) and labeled with the targeted approximate day/week.

As specified in the study protocol, laboratory data from scheduled visits are reported by central laboratories. The local results will not be used in the efficacy analyses or in the definition of

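### The objective to compare each sotagliflozin dose with placebo on HbA1c, FPG and body weight at Weeks 52 and 104 has no planned between-arm estimate, interval or missing-data method

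*SAP*

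**What the plan says.** The objective is comparative. SAP 1.2.3 reads "Other objectives of this study are to compare the effects of sotagliflozin 200 mg and 400 mg versus placebo with respect to", and the list that follows includes HbA1c, FPG and body weight at Weeks 52 and 104. Protocol 5.3 says the same.

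The planned analysis is not comparative. SAP 2.4.4.3 calls it descriptive, without formal testing: "Summary statistics at scheduled visits based on observed value will be provided by each treatment group". Protocol 11.4.2.3 agrees: "Summary statistics at scheduled visits using OC will be provided by each treatment group", where OC (observed cases) means "inclusion of only patients having nonmissing assessments at a specific visit" (Protocol 11.4). SAP 2.5.4 lists what is tabulated: "Summary statistics (number, mean, SD, SE, minimum, median, maximum) of continuous efficacy endpoints (observed data and change from Baseline) will be provided". SAP Appendix C gives ITT as the population for these endpoints and plans no supportive analysis.

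Values after treatment stop or rescue are kept. SAP 2.1.3 states: "All efficacy measurements collected during the study will be considered for analyses, including those obtained after IMP discontinuation or introduction of rescue therapy". SAP 1.1 expects patients who stop treatment early to remain in the study and be measured up to the last planned visit.

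BMD at the same visits is handled differently. SAP 2.4.5.1 plans multiple imputation and ANCOVA, giving the "adjusted mean change in BMD from Baseline to each timepoint (Week 26, Week 52, and Week 104) for each treatment group", together with the difference from placebo and its 95% CI. It also states that no significance tests will be done.

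**The concern.** The 78-week extension is there partly to provide long-term efficacy data, and the stated question is how each dose compares with placebo. By-arm summaries leave the reader to subtract one mean from another, with no adjustment for baseline, strata or country and no planned interval.

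They also change the population. SAP 2.4.4 places efficacy analyses in the ITT population, using values "including those obtained after IMP discontinuation or introduction of rescue therapy (de facto estimand), unless otherwise specified". A mean over patients who have a value at Week 104 describes those patients, not all who were randomized.

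The SAP does not close the gap elsewhere. SAP 2.5.4 says that efficacy values still missing after visit windowing are to be handled by multiple imputation, where appropriate, as set out in Section 2.4.4. Section 2.4.4 specifies endpoint imputation only for Week 26 (Week 12 for SBP). For Weeks 52 and 104 the cross-reference leads to no method.

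**Working it through.** **1. Inputs.** From SAP 1.3: 120 patients per arm, SD of HbA1c change 1.2%, planned difference -0.6% (400 mg versus placebo, Week 26), two-sided alpha 0.05, and a 30% missing rate stated for BMD only. The documents give no missing rate for HbA1c, FPG or body weight at Week 52 or 104, and no outcome for patients who are missing. Both are assumed below and shown as ranges.

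**2. The plan's own figure.** The standard error of the difference is 1.2 × √(2/120) = 0.155. Normal-approximation power is Φ(0.6/0.155 − 1.96) = 97.2%, and the noncentral t gives 97.1%. The stated 97% is reproduced and is not in dispute.

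**3. Bias of the observed-case difference.** Let d be the fraction missing in an arm, and g the mean HbA1c change of missing patients minus that of observed patients (positive means missing patients do worse). A and P denote sotagliflozin and placebo. Then

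bias = −dA·gA + dP·gP,

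and a negative value means the benefit is overstated.

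| dA | dP | gA | gP | bias (HbA1c points) |
|---|---|---|---|---|
| 0.3 | 0.3 | 0.6 | 0 | −0.18 |
| 0.3 | 0.3 | 0.3 | 0.3 | 0.00 |
| 0.3 | 0.3 | 0 | 0.6 | +0.18 |
| 0.2 | 0.2 | 0.6 | 0 | −0.12 |
| 0.2 | 0.2 | 0 | 0.6 | +0.12 |
| 0.2 | 0.3 | 0.3 | 0.3 | +0.03 |

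The sign depends on which arm loses its poorly controlled patients.

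**4. One special case.** The SAP's back-up washout method imputes missing sotagliflozin patients from placebo data. Suppose that holds, and missing placebo patients resemble observed placebo patients on average. If m is the fraction missing on sotagliflozin, the all-randomized difference is (1 − m) times the observed-case difference, so the overstatement is 1/(1 − m) − 1: 11% at m = 10%, 25% at 20% and 43% at 30%. This is the first row of the table when the observed-case difference is −0.60: −0.60 × 0.7 = −0.42, a gap of 0.18. These percentages follow from the assumption and are not evidence for it.

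**5. Would an interval be useful?** The unadjusted 95% half-width is t(0.975) × 1.2 × √(2/n), if the Week 26 SD carries over:

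| Missing per arm | n per arm | half-width (HbA1c points) |
|---|---|---|
| 0% | 120 | 0.31 |
| 20% | 96 | 0.34 |
| 30% | 84 | 0.37 |
| 40% | 72 | 0.40 |

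All are below the 0.6-point design difference, so an interval would be informative.

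**The case against.** The strongest reply is that the choice is deliberate and consistent. The ITT sentence in SAP 2.4.4 allows exceptions. The same section limits endpoints other than the primary and main secondary ones to descriptive statistics, and SAP 2.4.4.4 and Section 3 repeat this for analyses beyond Week 26. The objectives aim to demonstrate superiority on the confirmatory endpoints and only to compare effects on these. BMD is the key safety question and may merit more modelling. Each arm's n, mean and SE are tabulated, so a crude difference and interval can be derived. HbA1c summaries are repeated without post-rescue values, and Kaplan-Meier plots of treatment discontinuation and rescue are planned.

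Much of this stands. There is no breach of the test hierarchy, and readers are not wholly without a measure of uncertainty. But descriptive status does not explain the absence of an estimate: BMD has no test either, yet gets a difference and a CI at the same visits. A crude interval built from arm-level SEs is unadjusted and takes no account of missing patients.

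Two stronger readings are tempting, and neither is supported. First, a reader might infer that dropouts are excluded. Patients who stop treatment or are rescued but attend are included, and SAP 2.5.4 lets an unscheduled or early end-of-treatment value count if it falls in the visit window. Only patients with no value in the window are left out. Second, a reader might infer that the long-term effect is likely overstated. No dropout rates or reasons by arm are given, and Protocol 4.6 expects insufficient glucose control particularly on placebo. Losing those patients would understate the effect.

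**Conclusion.** The point holds as a gap between objective and analysis. A comparative objective at Weeks 52 and 104, in the ITT population, has no planned between-arm estimate, no CI and no missing-data method, while the SAP already specifies all three for the same endpoints at Week 26 and for BMD at Weeks 52 and 104.

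The direction of any bias is undetermined. For HbA1c it ranges from −0.18 to +0.18 points at 30% missing in both arms, and from −0.12 to +0.12 at 20%, if missing patients do worse by 0 to 0.6 points. Those missing rates and gaps are assumptions. The −0.6% and the SD of 1.2% are Week 26 planning values, used only for scale; they say nothing about 200 mg, FPG or body weight. The 11% to 43% overstatement applies only under the washout assumption and should not be read as an expected size.

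No confirmatory claim is affected. This is an inexpensive improvement that would let the trial answer its own long-term question.

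**What to change.** In SAP 2.4.4.3, for HbA1c, FPG and body weight at Weeks 52 and 104, add the ITT ANCOVA of 2.4.4.1 and 2.4.4.2 with the same imputation rule: retrieved dropouts, or washout if any arm has fewer than 5, judged at each visit. Report the adjusted difference of each dose from placebo with its 95% CI as an estimate only, without a test, and the number with no value by arm. Keep the observed-case tables as supportive. Extend the imputation text, now limited to Week 26 (Week 12 for SBP), to these visits so that the cross-reference in 2.5.4 leads to a method, and update Appendix C.

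The cost is SAP wording and some programming that reuses existing code at two more visits. It needs no new data and no alpha. The imputation brings its own assumption about missing patients, but one fixed in advance, and the resulting long-term estimate may differ from the observed-case means.

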2.4.4.4 Multiplicity issues

To control the family-wise type I error, a hierarchical testing procedure will be applied.

Once the primary variable (change from Baseline to Week 26 in HbA1c) is statistically significant at $\alpha = 0.05$ (2-sided), the following secondary efficacy variables will be tested in the following prioritized order. The testing will stop as soon as an endpoint is found not to be statistically significant at $\alpha=0.05$ (2-sided).

- Comparing sotagliflozin 400 mg versus placebo:
 - Change from Baseline to Week 26 in body weight,
 - Change from Baseline to Week 26 in FPG,
 - Change from Baseline to Week 12 in SBP for all patients.
- Comparing sotagliflozin 200 mg versus placebo:
 - Change from Baseline to Week 26 in HbA1c,
 - Change from Baseline to Week 26 in body weight,
 - Change from Baseline to Week 26 in FPG,
 - Change from Baseline to Week 12 in SBP for all patients.

No multiplicity adjustment will be made on efficacy variables other than those mentioned above.

In addition, no further multiplicity adjustment (split of alpha) is needed for multiple analyses (ie, first step and second step analyses see [Section 3](#)). The results of the first step analysis will not be used to change the conduct of the ongoing study in any aspect and all primary and secondary efficacy endpoints will be fully evaluable at the time of the first step analysis. Analyses beyond Week 26 will be descriptive.

2.4.5 Analyses of safety data

The summary of safety results will be presented by treatment group. The safety data will be summarized for the 26-week core treatment period and the 104-week entire treatment period separately, unless otherwise specified.

The observation period defined in [Section 2.1.4](#) is applicable in all safety analyses for classification of AEs, determination of treatment-emergent Potentially Clinically Significant Abnormality (PCSA) values and the last on-treatment value for laboratory, vital sign, BMD and ECG.

General common rules

All safety analyses will be performed on the safety population as defined in [Section 2.3.2](#), unless otherwise specified, using the following common rules:

- Safety data in patients who do not belong to the safety population (eg, exposed but not randomized) will be listed separately.

- The baseline value (with the exception of serum creatinine and eGFR) is defined as last available value before the first dose of double-blind IMP. For creatinine and eGFR, the baseline value is defined as the average of all values before the first dose of double-blind IMP.
- PCSA values are defined as abnormal values considered medically important by the Sponsor according to predefined criteria/thresholds based on literature review and defined by the Sponsor for clinical laboratory tests, vital signs, and ECG (Appendix A).
- PCSA criteria will determine which patients had at least one PCSA during the TEAE period, taking into account all evaluations performed during the TEAE period, including nonscheduled or repeated evaluations, central laboratory/reading or local measurements (see [Section 2.5.4](#)). The number of all such patients will be the numerator for the on-treatment PCSA percentage.
- The treatment-emergent PCSA denominator by group for a given parameter will be based on the number of patients assessed for that given parameter in TEAE period by treatment group on the safety population.
- For laboratory parameters cited in the protocol as efficacy endpoints (eg, HbA1c, plasma glucose, etc.), PCSA summaries will not be provided. These parameters will be summarized in efficacy [Section 2.4.4](#).
- For quantitative safety parameters based on central laboratory/reading measurements, descriptive statistics will be used to summarize results and change from Baseline values by visit and treatment group for the 104-week entire treatment period. Summaries will include the last on-treatment value. The last on-treatment value is commonly defined as the value collected at the same day/time of the last administration of IMP for the 104-week entire treatment period. If this value is missing, the last on-treatment value will be the closest value prior to the last administration of IMP during the 104-week entire treatment period.
- The analysis of the safety variables will be essentially descriptive and no systematic testing is planned. Relative risks versus placebo and their 95% confidence intervals may be provided, if relevant.
- Selected safety analyses will be summarized by age, gender, racial subgroups, and any pertinent subgroups (see details in [Section 2.4.5.3](#) and [Section 2.4.5.4](#)).

